Lens degeneration was observed microscopically with dose-related incidence and with minimal to moderate severity in males at \geq 30 mg/kg/day and minimal severity in males at 10 mg/kg/day and females at \leq 100 mg/kg/day (not identified in females at 300 mg/kg/day) ([Table 2](#)). Among the animals that have been evaluated microscopically, lens degeneration was identified in all animals that were noted to have cataracts on slit lamp examination.

Table 2: Microscopic examination of the eyes

Dose (mg/kg/day)	Males				Females			
	0	10	30	100	0	50	100	300
N (unscheduled deaths) ^a	15	15	15	15 (7)	15	15	15(1)	15
Lens degeneration:	0	1	3	9 (2)	0	1	2	0
Minimal	0	1	1	2 (1)	0	1	2	0
Mild	0	0	2	3	0	0	0	0
Moderate	0	0	0	4 (1)	0	0	0	0

N = Total number of animals examined.

a. Unscheduled deaths prior to ophthalmic examination in parentheses. The number of unscheduled deaths are included in the total number of animals (N).

The identification of cataracts in rats following 27-weeks of intermittent dosing represents new target organ toxicity. In the previous rat and dog repeat-dose toxicity studies up to 15 weeks duration, the primary target organ findings were observed in the hematolymphopoietic and male reproductive tissues. There were no PD-0332991-related ocular toxicities at doses up to 200 and 2 mg/kg/day in rats and dogs, respectively, in the 15-week toxicity studies (unbound systemic AUC exposures of 5200 and 684 ng•h/mL, respectively). In addition, no cataracts have been identified in PD-0332991-treated dogs at doses up to 3 mg/kg/day following 27-weeks of intermittent dosing (equivalent duration to that at which cataracts were observed in the rat study) using slit lamp ophthalmoscopy in an ongoing 39-week repeat-dose oral toxicity study (Study 8282225; Sponsor Reference Number 13LJ037; exposure data not available).

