A no observed effect level has not been identified for cataract formation from the 27-week rat toxicity study, based on the histological presentation of lens degeneration. The available data suggests that the lens degeneration observed at the lowest doses in both male and female rats is PD-0332991-related. Day 189 systemic AUC (total) exposure was 6000 ng•h/mL (750 ng•h/mL, unbound, based on Fu of 0.125 in the rat) and 2650 ng•h/mL (331 ng•h/mL, unbound) in males at 10 mg/kg/day and females at 50 mg/kg/day, respectively. These exposures are comparable to clinical exposure at the recommended human dose of 125 mg QD (unbound AUC 301 ng•h/mL). The mechanism for cataract formation in PD-0332991-treated rats is unknown; however, its pathogenesis may be related to primary pharmacology. CDK4 expression (mRNA and protein) has been identified in the lens epithelial layer and in lens fibers of rats, suggesting its importance to lens differentiation. Altered cell growth of the lens epithelium is also recognized as a potential mechanism for cataract formation.

In addition to the above toxicities, pulmonary toxicities of rales and dyspnea were observed in rats given oral doses > 300 mg/m². Histopathologic examination revealed accumulation of foamy alveolar macrophages and tracheal mucosal atrophy. In dogs, apnea occurred following intravenous (i.v) administration of PD-0332991 at a dose of 5 mg/kg that was attributed to central respiratory depression compounded by the effects of propofol induced general anesthesia. The in vitro Purkinje fiber and human ether -a-go-go (hERG) assays along with cardiovascular study in dogs given doses over 10 mg/kg indicate a risk for QT-interval prolongation. The IC₂₀ in the hERG assay was 1 µM (447.5 ng/mL) and QT prolongation occurring dogs was associated with a C_{max} > 211 ng/mL. No effects on ECG parameters were noted in dogs given 2 mg/kg in 3- or 15-week toxicity studies, with unbound C_{max} values (80 and 42 ng/mL respectively) that

exceeded those associated with human clinical dose of 125 mg QD (18 ng/mL).

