7 ADVERSE EVENTS: LIST AND REPORTING REQUIREMENTS

Adverse event (AE) monitoring and reporting is a routine part of every clinical trial. The following list of AEs (Section 7.1) and the characteristics of an observed AE (Sections [7.2](#) and [7.3](#)) will determine whether the event requires expedited reporting via the CTEP Adverse Event Reporting System (CTEP-AERS) **in addition** to routine reporting".

- Baseline Abnormalities

Any baseline (pretreatment) abnormalities observed during the initial physical examination should be recorded in the Rave database.

- Treatment or within 30 days of treatment

Only record Grades 1 and 2 adverse events if the attribution is at least possibly related to PD-0332991. Record all adverse events Grades 3 through 4 and deaths), regardless of attribution on the electronic case report forms.

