⁴Rash includes rash, rash maculo-papular, erythema, erythematous rash, erysipelas, rash pruritic, rash papular, generalized rash, exanthema, allergic dermatitis, dermatitis acneiform, and dermatitis.

⁵Peripheral neuropathy includes both peripheral motor neuropathy and peripheral sensory neuropathy under the NERVOUS SYSTEM DISORDERS SOC.

Adverse events reported on palbociclib (PD-0332991) trials, but for which there is insufficient evidence to suggest that there was a reasonable possibility that palbociclib (PD-0332991) caused the adverse event:

BLOOD AND LYMPHATIC SYSTEM DISORDERS - Bone marrow hypocellular; Blood and lymphatic system disorders - Other (pancytopenia)

CARDIAC DISORDERS - Atrial fibrillation; Cardiac arrest; Cardiac disorders - Other (paroxysmal atrial fibrillation with rapid ventricular response); Palpitations; Pericarditis; Sinus bradycardia; Supraventricular tachycardia

EYE DISORDERS - Cataract; Eye disorders - Other (retinal hemorrhage)

GASTROINTESTINAL DISORDERS - Abdominal distension; Abdominal pain; Ascites; Colitis; Colonic perforation; Dry mouth; Dyspepsia; Dysphagia; Esophageal stenosis; Flatulence; Gastric hemorrhage; Gastrointestinal disorders - Other (gastrointestinal hemorrhage); Intra-abdominal hemorrhage; Lower gastrointestinal hemorrhage; Small intestinal obstruction; Small intestinal perforation; Upper gastrointestinal hemorrhage

GENERAL DISORDERS AND ADMINISTRATION SITE CONDITIONS - Chills; Death NOS; Edema limbs; Localized edema; Malaise; Non-cardiac chest pain; Pain; Sudden death NOS

HEPATOBIILIARY DISORDERS - Hepatic failure; Hepatobiliary disorders - Other (bile duct obstruction); Hepatobiliary disorders - Other (jaundice)

IMMUNE SYSTEM DISORDERS - Allergic reaction

INJURY, POISONING AND PROCEDURAL COMPLICATIONS - Fall; Fracture

INVESTIGATIONS - Alkaline phosphatase increased; Blood bilirubin increased; CPK increased; Creatinine increased; Ejection fraction decreased; GGT increased; INR increased; Weight loss

METABOLISM AND NUTRITION DISORDERS - Dehydration; Hypercalcemia; Hyperglycemia; Hyperkalemia; Hypermagnesemia; Hyperuricemia; Hypoalbuminemia; Hypocalcemia; Hypokalemia; Hyponatremia; Hypophosphatemia; Metabolism and nutrition disorders - Other (failure to thrive)

MUSCULOSKELETAL AND CONNECTIVE TISSUE DISORDERS - Arthralgia; Back pain; Flank pain;

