
A. CBC with differential at baseline and q weekly during each cycle for the first 3 cycles; consideration can be given to increase interval to q 2 weeks from course 4 onwards if the patient has no DLT in the previous cycle. If patient develops Grade 4 neutropenia or thrombocytopenia, then CBCs should be checked every 3-4 days until recovery to Grade 3.
 
B. Within 48 hours of beginning protocol therapy and each course (see 5.3).
 
C. 12-lead EKG at baseline, and 3 hours post dose on days 1, 8, and 15 of cycle 1 and on day 1 of cycles 2 and 3. Thereafter, EKG should be done prior to the start of every 3rd cycle (prior to 6, 9, 12, 15, 18, 21, 24 and end of treatment).
 
D. Eye exam is to be done at baseline, and every 3 months (after courses 3, 6, 9, 12, 15, 18, 21, 24). The ophthalmology exam report should clearly specify the presence or absence of cataracts and data must be recorded in Rave database.
 
E. Standard imaging is to be done every 8 weeks (after courses 2, 4, 6) and then every 12 weeks thereafter through the 26 courses and at the completion of treatment.
 
F. MRI Spine should be done at the same time points as the standard MRI brain, if clinically indicated.
 
G. 2 unstained slides from FFPE block and 1 H&E slide required to be submitted for Rb testing (see 9.1.1)
 
H. Obtain 5 mL of whole blood prior to 1st dose if consented (See section 9.2.1 for details)
 
I. Plasma PK (required) – D1 Course 1: pre-dose, 0.5, 1, 2, 4, 8, 10, 24, 48 hrs after dose D21 Course 1: pre-dose, 1, 2, 4, 8, 10, 24 after dose (See section 9.2.2 for details of Plasma PK) Plasma PK after discontinuation of dexamethasone (if consented) – see section 9.2.2
 
J. 10 unstained slides from FFPE block or FFPE tissue block [See section 9.3.3 for details of Pre-trial tumor materials for Genomics (if consented)]
 
K. Biorepository samples (if consented) – 20 unstained FFPE slides and blood. Obtain 2-5 mL of whole blood at baseline. If unable to collect at baseline, it can be collected any time during protocol therapy. See section 9.3.1 for details.
				

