Hispanic or Latino	5	+	6	= 11
Not Hispanic or Latino	22	+	22	= 44
Ethnic Category: Total of all subjects	27	+	28	= 55
Racial Category				
American Indian or Alaskan Native	0	+	0	= 0
Asian	3	+	3	= 6
Black or African American	6	+	7	= 13
Native Hawaiian or other Pacific Islander	0	+	0	= 0
White	18	+	18	= 36
Racial Category: Total of all subjects	27	+	28	= 55

13.4 Analysis of the Adverse Event Data:

All patients who receive at least 1 dose of protocol therapy will be included in the safety analyses. Adverse event data will be summarized in stratum specific tables which will incorporate dose, attribution as well as grade information.

13.5 Data analysis plan for the secondary objectives:

Any objective responses (PR+CR) which may be observed in this trial will be described by dose and by histology. We will also report prolonged disease stabilizations in a descriptive fashion.

The biology and PD/PG studies are optional in this trial and thus data will be available only from a subset of patients who are likely to represent a variety of histologies. The data generated as part of these correlative studies will be described and summarized in an exploratory fashion via summary statistics and frequency tables as appropriate.

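### The planned safety tables use only attribution-filtered adverse events, so a new low-grade cataract recorded at a slit-lamp exam can be missing from all of them

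*Combined protocol and SAP*

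**What the plan says.** **The signal.** Section 2.2.2.1 reports no no-effect level for the lens finding in the 27-week rat study and states: "The available data suggests that the lens degeneration observed at the lowest doses in both male and female rats is PD-0332991-related". On exposure at those lowest doses it adds: "These exposures are comparable to clinical exposure at the recommended human dose of 125 mg QD (unbound AUC 301 ng•h/mL".

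**The response.** Section 3.3.8 excludes patients with cataract and asks that the baseline report state cataract status by slit lamp. The study calendar (Section 10) lists an ophthalmology exam including slit lamp. Footnote D places it at baseline and after courses 3, 6, 9, 12, 15, 18, 21 and 24, and requires: "The ophthalmology exam report should clearly specify the presence or absence of cataracts and data must be recorded in Rave database". That entry carries no grade or attribution condition.

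**What becomes an adverse event.** The opening of Section 7 says: "Only record Grades 1 and 2 adverse events if the attribution is at least possibly related". Grade 3 and 4 events and deaths are recorded whatever the attribution. Section 7.4 says that all adverse events go into the routine data submissions and sets no limit by grade or attribution.

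**What is tabulated.** Section 13.4 covers everyone who received at least one dose and says: "Adverse event data will be summarized in stratum specific tables which will incorporate dose, attribution as well as grade information". Neither Section 13.4 nor Section 13.5 mentions the eye-exam results.

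**The concern.** The protocol treats cataract as a risk worth screening for and following with repeated exams, and describing toxicities is part of primary objective 1.1.1. Yet the planned safety summary is built from adverse event records, and for Grades 1 and 2 such a record depends on the site's causality judgement.

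That filter is not needed for this event. Baseline cataract is excluded, so any cataract seen at a later exam is new on study. An exam-based count is available without asking anyone about cause. If the plan is followed as written, the exam field is collected and not used, and a reader of the tables could take a low or zero cataract count as the result of the slit-lamp surveillance when it is not.

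**Working it through.** **Step 1: the exposure comparison.** Unbound AUC = total AUC × unbound fraction, "based on Fu of 0.125 in the rat".
- Males, 10 mg/kg/day: 6000 × 0.125 = 750 ng·h/mL (stated 750). Ratio to human 301: 750/301 = 2.49.
- Females, 50 mg/kg/day: 2650 × 0.125 = 331.25 ng·h/mL (stated 331). Ratio: 331.25/301 = 1.10.

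The stated figures reproduce. The description as comparable is close for females and looser for males.

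**Step 2: what was seen at those doses.** Section 2.2.2.1 has two different endpoints.

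| Endpoint | Males 0 / 10 / 30 / 100 mg/kg/day | Females 0 / 50 / 100 / 300 mg/kg/day |
|---|---|---|
| Slit-lamp cataract (Table 1) | 0/20, 0/20, 2/20, 9/13 | 0/20, 0/20, 0/19, 0/20 |
| Microscopic lens degeneration (Table 2) | 0/15, 1/15, 3/15, 9/15 | 0/15, 1/15, 2/15, 0/15 |

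At the lowest dose in each sex, lens degeneration was 1/15 against 0/15 (Fisher p = 1.0). The drug-related reading therefore rests on the trend in males, whose top dose gives p = 0.0007 against control. Slit-lamp cataract, the endpoint that patients are examined for, was 0/20 in each sex at the lowest dose. Pooling these as 0/40, the exact one-sided 95% upper limit is 1 − 0.05^(1/40) = 7.2%.

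**Step 3: the path of a new cataract found at a scheduled exam.**

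| Case | Eye-exam entry in Rave (footnote D) | Adverse event record (Section 7 opening) | Section 13.4 tables |
|---|---|---|---|
| Grade 3 or 4, any attribution | Yes | Yes | Yes |
| Grade 1 or 2, at least possibly related | Yes | Yes | Yes |
| Grade 1 or 2, unlikely or unrelated | Yes | No | No |

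If Section 7.4 is taken literally, the third case becomes an adverse event record and reaches the tables. The two sections give different answers, and the protocol does not say which governs.

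**Step 4: size.** The expected number missing from the tables is N × p × g × q, where N is the number of patients examined, p the chance of a new cataract, g the share that are Grade 1 or 2, and q the share of those judged unlikely or unrelated. The documents give none of p, g or q for patients. As q runs from 0 to 1, the loss runs from none to all of the low-grade cataracts. No narrower figure can be supported.

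**The case against.** The strongest reply is that nothing is lost. Footnote D puts every cataract found at a scheduled exam into Rave, the baseline exclusion makes each one identifiable as new, and an analyst could list them without a protocol change. Section 7.4 can also be read as requiring all adverse events. The protocol's own account of the rat data and the eye-exam schedule may lead sites to choose the possible category in any case. The animal evidence is mixed too. Section 2.2.2.1 reports no drug-related ocular toxicity in the 15-week rat study at an unbound AUC of 5200 ng·h/mL (5200/301 = 17 times the human value), and no cataract in dogs after 27 weeks.

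Most of this stands, and it limits the point to reporting. It does not close the gap: being able to tabulate a field is not the same as planning to, and the conflict between Sections 7 and 7.4 remains.

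Three stronger readings are tempting, and the documents do not support them.
- A reader might take 1/15 as a cataract rate and compute how many cases would go unreported. That figure is microscopic lens degeneration, the matching slit-lamp count is 0/20 in each sex, and any share judged unrelated would be invented.
- A reader might infer that the adverse event list in Section 7.1, with its entry "EYE DISORDERS - Cataract; Eye disorders - Other (retinal hemorrhage" among events with insufficient evidence of causation, pushes sites towards unrelated. That list summarises reports from human trials, so it does not contradict a rat study. Attribution is set on the five-category scale in Section 7.2, which leaves possible open.
- A reader might infer a stronger filter in heavily pretreated stratum II. Nothing in the documents links prior therapy to cataract attribution, and stratum I also allows focal radiotherapy and up to four regimens.

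**Conclusion.** The point holds as a gap between collection and analysis. Under the Section 7 recording rule and Section 13.4 as written, a Grade 1 or 2 cataract that is new on study and judged unlikely or unrelated can be absent from every planned safety table, although its presence is recorded in Rave. Sections 7 and 7.4 also disagree on which adverse events are recorded.

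The size of any undercount is unknown and may be zero. The conclusion rests on two assumptions: that sites follow the opening of Section 7 and not a literal reading of Section 7.4, and that at least one low-grade cataract occurs and is judged not related. It does not mean that cataracts disappear from the trial data, and it makes no claim about the cataract rate in patients.

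**What to change.** 1. **Section 13.4.** Add a table of new-onset cataracts taken from the slit-lamp results already in Rave, by stratum and dose, at any grade, for all treated patients with a post-baseline exam. Show attribution where it is available, but do not use it to select cases. Give the number examined in each cell. The first scheduled follow-up exam is after course 3 and the calendar lists none at discontinuation, so some treated patients may have no post-baseline result.
2. **Sections 7 and 7.4.** Reconcile them so that one rule states which adverse events are recorded.
3. **Section 2.3.1 (editorial only).** It places cataracts and lens degeneration above 30 mg/kg/day. Section 2.2.2.1 reports cataract at 30 mg/kg/day and above, and lens degeneration from 10 mg/kg/day. No analysis depends on this.

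The cost is one table and one clarifying sentence, with no new exam. Because the table uses data already required of everyone, it treats closed stratum I (21 enrolled as of version 8.0) and stratum II (4 enrolled at that point) under the same rule. Changing the adverse event recording rule for future patients alone would not do that. The downside is that a few cataracts from other causes will be listed.

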2.2.2.2 Pre-clinical Pharmacology

PD-0332991 was given via oral and i.v routes to Sprague-Dawley rats, Beagle dogs, and Cynomolgus monkeys. The PK parameters following single dose administration are given in [Table 3](#). In general, mean plasma clearance values were low to moderate in all species and volume of distribution at steady state was about 10 fold greater than total body water indicating drug distribution into peripheral tissues.

Table 3

Species (Strain)	Dose (mg/kg)	Route (n)	C _{max} (mg/mL)	T _{max} (h)	t _{1/2} (h)	CL (mL/min/kg)	V _{ss} (L/kg)	AUC _(0-∞) (μg·h/mL)	F (%)
Rat (Sprague-Dawley)	1	IV ^a (3)	NA	NA	2.2 (0.34)	38.0 (3.79)	5.65 (0.736)	0.442 (0.0467)	NA
	5	IV ^a (3)	NA	NA	2.6 (0.19)	37.4 (1.58)	7.07 (0.317)	2.23(0.103)	NA
	5	PO ^b (3)	0.178 (0.0474)	3.5 (1.9)	2.1 (0.12)	NA	NA	1.20 (0.393)	56.1 ^c
	20	PO ^b (3)	1.11 (0.0618)	5.0 (1.2)	2.8 (0.36)	NA	NA	10.8 (0.651)	ND
	50	PO ^b (3)	1.66 (0.245)	4.5 (1.9)	4.9 (1.4)	NA	NA	23.0(6.74)	ND
	200	PO ^b (3)	2.24 (0.166)	30 (0)	NC	NA	NA	76.8 ^d (8.9)	ND
Dog (Beagle)	1	IV ^a (3)	NA	NA	11 (0.29)	7.22 (0.853)	6.22 (0.789)	2.33 (0.258)	NA
	20	PO ^b (3)	0.664 (0.247)	8.7 (3.1)	21 (5.7)	NA	NA	17.4±6.9 ^e	36.9 (12.4) ^f
Monkey (cynomolgus)	0.5	IV ^a (3)	NA	NA	4.7 (1.4)	13.4 (0.896)	5.05 (1.01)	0.624 (0.0428)	NA
	2.66	PO ^b (3)	0.0862 (0.0231)	2.7 (1.2)	5.3 (0.89)	NA	NA	0.768 (0.150)	23.1 (3.6)

Note: Values in parentheses indicate "± standard deviation."

AUC_(0-∞) = AUC from time zero extrapolated to infinity.

F (%) = Absolute (oral) bioavailability.

NA = Not applicable.

ND = Not determined.

NC = Not calculated—the concentration time-profile would not allow calculation of t_{1/2}.

^aIn solution (5% DMA/25% Propylene glycol/70% D5W).

^bIn suspension for rat and monkey (5%/5% PEG200/0.5% methylcellulose), and by capsule for dogs.

^cF was calculated when IV and PO doses were equivalent, based on mean AUC_(0-∞) after IV and PO administration.

^dValue represents AUC_(0-t), because the concentration time-profiles would not allow calculation of AUC_(0-∞).

^eValue represents AUC_(0-t), because the AUC_(0-∞) was extrapolated >20% and thus not reported.

^fAbsolute oral bioavailability calculated using AUC_(0-t) value following PO administration, because the AUC_(0-∞) was extrapolated >20%.

PK parameters following multiple dosing of PD-0332991 in the same species is given in [Table 4](#).

The C_{max} and AUC values increased in a dose-related manner in all species. There was gender related differences in rats (higher rates of clearance in females compared to males). Dose accumulation (3-fold) was observed following multiple dosing both rats and dogs.

Table 4

Species	Study Day	Dose (mg/kg/day)	C _{max} (ng/mL)		AUC ₍₀₋₂₄₎ (ng·h/mL)	
			Male	Female	Male	Female
Rat ^a	1	30	ND	211	ND	887
		100	ND	291	ND	2960
		300	3250	2400	50500	37300
		600	3140	ND	64400	ND
	8	300	5620	ND	104000	ND
		14	30	ND	191	ND
	100		ND	403	ND	3170
	300		ND	634	ND	9370
	1	50	1170	ND	18600	ND
		100	1740	306	30900	2050
		200	1710	435	35200	4090
		400	ND	319	ND	4850
	21	50	1800	ND	17300	ND
		100	2220	296	45300	2530
		200	2310	494	46600	5930
		400	ND	954	ND	11100
			Male and Female		Male and Female	
Dog	1 ^b	1	26.0±3.45		392±79.7	
		3	119±17.1		1890±197	
		10	449±194		7720±3530	
		20	559±280		9630±4860	
		40	560±197		9430±2970	
	9 ^c	10	1120		24500	
		20	849		18900	
		40	1250		25600	
	14 ^b	1	59.5±14.1		992±186	
		3	313±28.6		5700±466	
	1 ^b	0.2	6.96±1.68		106±29.3	
		0.6	18.0±3.52		279±59.2	
	21 ^b	2	80.6±15.2		1150±202	
		0.2	12.2±3.18		206±63.7	
		0.6	35.3±8.72		581±143	
			2	193±35.3		3260±861

ND = Not determined.

^aToxicokinetic parameters were derived from composite plasma concentration-time profiles in rats, standard deviation (SD) not calculated.

^bC_{max} and AUC values presented as mean±SD.

^cN = 1 female, SD not calculated.

2.2.3 Adult Clinical Trials

2.2.3.1 Phase I trial of PD-0332991 in adults with recurrent solid tumors
PD-0332991 has been tested in a Phase I trial in adults with recurrent solid tumors and lymphomas (A5481001) that explored two different schedules of the drug. In the first schedule reported by Schwartz et al., adult patients with Rb1 positive recurrent solid tumors were enrolled

across four cohorts using doses of 100 mg, 150 mg, 200, and 225 mg given orally daily for 14 days every 3 weeks (Schedule 2/1).³ No DLTs were observed at the 100 mg or 150 mg dose level. Dose limiting myelosuppression occurred in 2/3 patients at the 225 mg dose level [Grade IV neutropenia and thrombocytopenia (n=1) and Grade III neutropenia with delayed recovery (n=1)]. An intermediate dose of 200 mg/day was chosen. After only one DLT was observed (Grade III neutropenia and thrombocytopenia) in 6 enrolled patients at this dose, the cohort was expanded to a total of 20 patients. Three additional patients suffered DLT (Grade III myelosuppression with delayed recovery) with an overall 20% rate of DLT at this dose level. Since this did not exceed the preset limit of 33%, 200 mg/day for 14 days every 4 weeks was declared the MTD. Additional toxicities were mild and included Grade I fatigue and Grade I-II diarrhea. No patient had Grade 3 prolongation of QTc interval on EKG during therapy. Plasma PK studies revealed a dose proportional increase in C_{max} and AUC_{0-10} on days 1 and 8. In samples obtained from patients receiving 200 mg q daily, repeated dosing led to steady state levels. The median T_{max} was 4.2 hours and volume of distribution was 3241 liters (more than the adult total body water of 42 liters) suggesting extensive tissue penetration. PD-0332991 was eliminated slowly with a mean $T_{1/2}$ of 26.7 hours.²¹ One patient with a non-seminomatous germ cell tumor of the testis achieved a prolonged partial response and 9 had SD. Six patients with SD had treatment for ≥ 4 cycles and 2 for ≥ 10 cycles.

In the second schedule of the same Phase I study, daily treatment for 21 days every 4 weeks (Schedule 3/1) was evaluated in 41 adult patients with recurrent Rb1 positive solid tumors.²² Dose levels studied included 25, 50, 75, 100, 125 and 150 mg orally once daily. Five DLTs (either Grade III or IV neutropenia) were observed; 2 at 75 mg, 1 at 125 mg, and 2 at 150 mg. Thus 125 mg was declared the MTD. In an expanded cohort of 22 patients at this dose level, only 2 additional patients suffered Grade III neutropenia, making this the recommended Phase II dose. Additional toxicities were mild and included nausea, fatigue, and diarrhea. There was only one instance of a mild QTc prolongation in one patient that was felt not related to study drug. Plasma PK study results were similar to the previous Phase I trial.

2.2.3.2 Phase II trial of PD-0332991 in adults with recurrent mantle cell lymphoma and breast cancer

A Phase II trial of PD-0332991 was recently reported in adults with recurrent mantle cell lymphoma (a tumor that has aberrant cyclin D1 expression and homozygous loss of CDKN2A and hence dysregulation of the cell cycle signaling pathway).²⁴ Seventeen patients (median age, 66 years) were treated with PD-0332991 at 125 mg orally once daily for 21 days every 4 weeks until disease progression or unacceptable toxicity. The treatment was well tolerated and most Grade III or IV events were neutropenia or thrombocytopenia. No patient came off study for toxicity. The objective response rate was 18% (PR 2, CR 1) in 16 evaluable patients. An additional 7 patients experienced stable disease. Objective responses were observed between 4-8 cycles. Three patients have had prolonged stable disease on treatment between 565 – 903+ days. Five patients received study drug for more than one year. Six patients suffered PD. Evaluable lymph node biopsies in 10 paired tumor samples (done before and after 21 days of treatment) showed significant reduction of phosphor-RB (pS807/811) [mean, 89% (range, 51.6-100)] although total Rb1 staining was preserved. There was also similar reduction of Ki-67 staining (mean, 78%, range, 5-98.2%). Degree of reduction of phosphor-RB correlated with that of Ki-67.

All patients had Fluoro-deoxy glucose (FDG) PET and Fluoro-thymidine (FLT) scans at baseline and demonstrated avid tumor uptake of both FDG and FLT. Sixteen patients had both a baseline and post-treatment scans (day 21) for evaluation. The 3 patients who had objective responses demonstrated significant reduction (> 80%) of FLT uptake and a 24% decrease in FDG. Even patients who had SD or PD by routine imaging demonstrated > 25% reduction in both PET studies.²⁴

In a randomized Phase I/II trial of PD-0332991 in combination with letrozole vs. letrozole alone as first-line treatment in 165 post-menopausal women with ER+/HER2- advanced breast cancer, preliminary analysis of median progression-free survival (PFS) was significantly higher in patients receiving PD-0332991 plus letrozole vs. letrozole alone (26.2 vs. 7.5 months respectively) with a hazard ratio (HR) = 0.32 (95% CI 0.19-0.56).²⁸ The most commonly reported treatment-related adverse events included neutropenia, leucopenia, anemia, and fatigue.

